9.6 Data Collection and Management

9.6.1 Data Collection

A Web-based electronic data capture (EDC) system will be used in this study for physicians who complete the survey via the Internet or a telephone interview. An invitation will be sent via e-mail or made by phone to the selected sample of physicians, inviting them to participate and providing a link to the Web-based questionnaire. An option for a telephone interview will be offered to physicians who prefer this mode of survey administration.

For physicians who elect to complete the questionnaire via the Internet, each invited physician will be asked to log in to the study Web site by entering a unique identification number and password assigned to each participant and provided in the invitation to participate. The questionnaire will begin with an electronic informed consent. After participants consent, they will be prompted to complete the questionnaire.

For physicians who elect to complete the questionnaire via a telephone interview, the interviewer will enter a unique identification number assigned to each participant into the EDC system. Prior to administering the questionnaire, the interviewer will obtain a verbal informed consent. After participants consent, the interviewer will administer the questionnaire.

The questionnaire (closed-ended questions with predefined answers) can be completed at the participants' convenience. Although participants will be encouraged to complete

the questionnaire in a timely manner, once they start the questionnaire via the Internet, they will be able to stop at any point and, at a later time, pick up where they left off, should that be necessary. Participants will not be able to go back and change answers to previous questions. This restriction minimises the likelihood of the respondent searching for answers via the Web or other sources or being influenced by answers to subsequent questions. Participants who elect to complete the questionnaire via a telephone interview will also be encouraged to complete the questionnaire during one telephone interview.

Participants will also not be allowed to regain access to the questionnaire once it has been completed. Based on potential country-specific requirements, the recruitment process and physician questionnaire may be different between countries. Country-specific differences will be described and appended to the final study protocol.

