Stop using Diane-35 or its generics for at least 2 weeks in advance of a major surgery or a required period of prolonged immobilisation			
Stop using Diane-35 or its generics for at least 4 weeks in advance of a major surgery or a required period of prolonged immobilisation	 *		
Use a non-hormonal treatment for their skin condition and, if necessary , a non-hormonal method of contraception during this time	 *		
Resume treatment with Diane-35 or its generics at 1 week after complete remobilisation			
Resume treatment with Diane-35 or its generics at 2 weeks or later after complete remobilisation	 *		

Q14. Diane-35 and its generics are contraindicated in which of the following patient populations?

Tick Yes, No, or I don't know for each patient population listed.

Population	Yes	No	I don't know
Patients who are currently using another hormonal contraceptive	 *		
Patients who have a current or history of a thromboembolic event (e.g., deep vein thrombosis, pulmonary embolism, myocardial infarction, cerebrovascular accident, transient ischaemic attack, angina pectoris)	 *		
Patients with a history of childhood asthma			
Patients who have knowledge of a predisposition for a blood clotting disorder	 *		
Patients with a history of migraine with aura	 *		
Patients with moderate anaemia			
Patients with diabetes mellitus and concurrent vascular complications	 *		
Patients with hypertension (e.g., systolic \geq 160 or diastolic \geq 100 mm Hg)	 *		

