Patients with dyslipidemia	 *		
Patients who have had a recent major surgery	 *		
Patients who are experiencing or expected to experience a period of prolonged immobilisation	 *		

Q15. Which of the following risk factors for the development of thrombosis should be considered prior to prescribing Diane-35 and its generics? Tick Yes, No, or I don't know for each risk factor listed.

Risk Factor	Yes	No	I don't know
Body mass index over 30 kg/m ²	 *		
Age greater than 35 years	 *		
Smoker	 *		
Hypertension (i.e., systolic 140-159 or diastolic 90-99 mm Hg)	 *		
The patient has a close relative (e.g., parent or sibling) who has had a thromboembolic event at a young age (e.g., before 50)	 *		
History of renal calculus (kidney stone)			
Patient or someone in her immediate family has dyslipidemia	 *		
History of migraines	 *		
A cardiovascular condition such as atrial fibrillation, arrhythmia, coronary heart disease, cardiac valve disease	 *		
Diabetes mellitus	 *		
Chronic lassitude			
Practicing sports under no medical supervision			
Given birth in the last few weeks	 *		

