Medical conditions that might increase the risk of thrombosis (e.g., cancer, systemic lupus erythematosus, sickle cell disease, Crohn's disease, ulcerative colitis, haemolytic uraemic syndrome)	 *		
Use of other medicines that can increase the risk of thrombosis (e.g., corticosteroids, neuroleptics, antipsychotics, antidepressants, chemotherapy)	 *		

Q16. What is the prescribing guidance on the use of Diane-35 or its generics for women who smoke?

Tick Yes, No, or I don't know for each prescribing guidance.

Prescribing Guidance	Yes	No	I don't know
Women who are greater than 35 years of age should strongly be advised to stop smoking or use a non-hormonal treatment for her acne and/or hirsutism	 *		
Women who are greater than 35 years of age and			

smoke can be prescribed Diane-35 and should be warned about potential risks of thrombosis			
Women of any age don't need to be advised to stop smoking if they smoke less than 5 cigarettes a day			

**Q17. Which medical conditions can increase the risk of thrombosis?
Tick Yes, No, or I don't know for each medical condition listed.**

Medical Condition	Yes	No	I don't know
Cancer	 *		
Diabetes mellitus	 *		
Systemic lupus erythematosus	 *		
Haemolytic uraemic syndrome	 *		
Urinary tract infection			
Chronic inflammatory bowel disease (e.g., Crohn's disease or ulcerative colitis)	 *		
Asthma			
Sickle cell disease	 *		

**Q18. A patient should be advised to seek immediate medical attention for which of the following symptoms of a possible deep vein thrombosis?

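### In the Annex 3 questionnaire, a Q15 row states as fact the answer to 5 of the 6 Yes-keyed rows of Q17, so Q17 results for those rows mix knowledge with cueing and can only be pushed upward

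*Protocol*

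**What the plan says.** Section 9.3 of the protocol says that the final questionnaire is in Annex 3, so item wording and order are fixed there.

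- **Q15** asks "Which of the following risk factors for the development of thrombosis should be considered prior to prescribing Diane-35 and its generics". It has 15 rows: 12 keyed Yes and 3 distractors (kidney stones, chronic lassitude, unsupervised sport). The next-to-last row begins "Medical conditions that might increase the risk of thrombosis (e.g., cancer, systemic lupus erythematosus, sickle cell disease" and continues the list with Crohn's disease, ulcerative colitis and haemolytic uraemic syndrome. Diabetes mellitus is a separate row.
- **Q16**, on smoking, comes next.
- **Q17** then asks "Which medical conditions can increase the risk of thrombosis". It has 8 rows. Six are keyed Yes: cancer, diabetes mellitus, systemic lupus erythematosus, haemolytic uraemic syndrome, inflammatory bowel disease and sickle cell disease. Two are distractors: urinary tract infection and asthma.

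On navigation, Section 9.6.1 says "Participants will not be able to go back and change answers to previous questions". Its stated reasons are to deter looking up answers and to keep respondents from "being influenced by answers to subsequent questions". Section 9.7 has each question analysed on its own among those who answer it. Section 9.9 names drop-out by physicians who cannot answer as a way in which knowledge could be overestimated. It does not mention one item cueing another.

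**The concern.** The Q15 row does not ask whether these diseases raise thrombosis risk. It says that they do, and asks whether such diseases should be considered before prescribing. A physician who did not know that haemolytic uraemic syndrome or sickle cell disease belongs on the list has just read that it does, and is then asked exactly that.

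The protocol recognises contamination between items but blocks it in one direction only: later questions cannot alter earlier answers. Nothing covers the forward direction.

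Risk factors for thromboembolism are one of the named knowledge objectives (Section 8), and Q17 is the only question that tests these less obvious diseases one by one. Because questions are reported individually, a cued row would be reported as knowledge. Physicians who never received the educational material see the same content in Q15, so a correct Q17 answer says less than it should about what they knew beforehand. Later analysis cannot recover the answers that would have been given without the cue.

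**Working it through.** **Step 1. The plan's own precision figures.** Table 1 gives exact (Clopper-Pearson) 95% limits. All 16 rows reproduce to one decimal. At n=500:

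- 85% correct: 81.6 to 88.0, half-width (88.0 − 81.6)/2 = 3.2 points
- 80% correct: 76.2 to 83.4, half-width (83.4 − 76.2)/2 = 3.6 points

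These figures are correct. They serve here only as a yardstick.

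**Step 2. Q17 set against Q15.**

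| Q17 row | Key | In Q15? |
|---|---|---|
| Cancer | Yes | Stated as true |
| Systemic lupus erythematosus | Yes | Stated as true |
| Haemolytic uraemic syndrome | Yes | Stated as true |
| "Chronic inflammatory bowel disease (e.g., Crohn's disease or ulcerative colitis") | Yes | Both diseases stated as true |
| Sickle cell disease | Yes | Stated as true |
| Diabetes mellitus | Yes | Asked as a row, not stated |
| Urinary tract infection | not keyed | Absent |
| Asthma | not keyed | Absent |

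Five of the six keyed rows (83%) are given away and neither distractor is. A respondent with no prior knowledge who simply repeats the Q15 examples gets five of six keyed rows right. Asthma has been seen before, in Q14 as "Patients with a history of childhood asthma", but there it is an unkeyed option in a Yes/No grid and nothing about it is stated.

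**Step 3. Direction and size.** For one cued row, let p be the share who would tick Yes without the cue, and c the share of the others who tick Yes because of it. Then

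observed = p + (1 − p)c, so inflation = (1 − p)c.

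This is zero if c = 0 and positive otherwise. The protocol gives no value for c, so the values below are assumptions. For p, Table 1's planning values of 80% and 85% are used.

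| Assumed c | p = 80% | p = 85% |
|---|---|---|
| 10% | 0.20 × 0.10 = 2.0 points | 0.15 × 0.10 = 1.5 points |
| 25% | 0.20 × 0.25 = 5.0 points | 0.15 × 0.25 = 3.75 points |
| Half-width, n=500 | 3.6 points | 3.2 points |

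At c = 10% the inflation is inside the planned half-width. At c = 25% it is outside.

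**Step 4. Read backwards from an observed 85%.** Solving for p gives p = (0.85 − c)/(1 − c):

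- c = 10%: 0.75/0.90 = 83.3%
- c = 25%: 0.60/0.75 = 80.0%

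The true value falls below the lower limit of 81.6% once c exceeds (0.85 − 0.816)/(1 − 0.816) = 0.034/0.184, about 18%. A larger sample narrows the interval but leaves the inflation unchanged.

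**The case against.** Several counter-arguments have weight.

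- **Q17 still measures knowledge.** A reader might infer that Q17 only tests recall of the preceding screens. The documents do not support that. Physicians who already know the answer are right either way, Q16 intervenes, the screen layout is not described, some respondents answer by telephone, and web respondents may pause. Each of these could weaken the cue. None removes it.
- **Not every keyed row is given away.** It is tempting to count diabetes as cued because it also appears in Q15. It is only asked there, in a grid with distractors, and being listed does not reveal the key. The count is five of six.
- **A large bias is not shown.** One can reach inflation of tens of points by assuming low true knowledge and high cue uptake. Neither input is in the protocol, and at its own planning values with 10% uptake the effect is 1.5 to 2.0 points.
- **The last two Q15 rows are not empty.** They offer diseases, and medicines, that raise thrombosis risk as risk factors for thrombosis, so one might say that they carry no information. But the Q15 stem asks what should be weighed before prescribing, and both rows follow the Prescribers' Checklist closely. They are leading, and no more than that can be said.
- **The reach is limited.** Q17 is one of 14 knowledge questions (Q8 to Q21), other items also cover risk factors, and the protocol sets no success threshold and defines no summary score.

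These arguments limit the size and reach of the point. The overlap, its direction and the lack of a safeguard all stand.

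**Conclusion.** The point holds for five rows of one question. Q15 supplies the answers to five of Q17's six Yes-keyed rows, no stated safeguard covers cueing in that direction, and any resulting bias in those rows is upward. This rests on the annexed wording and order, and on respondents seeing the questions in numerical order.

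The size is unknown. The 1.5 to 5.0 points are illustrations: they assume 80-85% correct without the cue and uptake of 10-25%. They show that the bias could be negligible or could exceed the planned sampling error at n=500. The study-size calculation is unaffected. The change is worth making because it is simple and the analysis cannot repair the problem afterwards.

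**What to change.** Ask Q17 before Q15 in the web tool and the telephone script. Q17 has its own distractors and does not state its key, so moving it forward does not create the same problem in reverse. No new wording or extra respondents are needed. Deleting the examples from the Q15 row is a weaker alternative: what remains is a barer and more leading row, and diabetes still appears in Q15.

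The cost is an update to every language version and possibly a notification to the reviewing bodies. The questionnaire was pretested with 25 physicians (Section 9.4.1), and the timeline in Section 6 includes regulatory approval of the questionnaire as well as IRB and CNIL steps. Because Section 6 lets Austria, the Czech Republic and the Netherlands start before France and Spain, the change should be in place before the first country opens, so that all countries use the same order.

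If the order cannot be changed, report the five rows as cued by Q15 and as likely upper estimates of knowledge, add this to the limitations in Section 9.9, and note that the last two Q15 rows are leading.

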- A prescriber checklist of contraindications for the use of Diane-35 in the context of thromboembolism

The educational material is being distributed to health care professionals who are expected to prescribe Diane-35 or its generics. Distribution started in July 2014. Specific timing may vary by country based on regulatory approvals of the educational materials in local language versions.

In collaboration with Bayer, we have developed this protocol for a joint, observational post-authorisation safety study (PASS) with the purpose of assessing physician knowledge and understanding of the key safety information outlined by the PRAC and included in the Diane-35 educational material developed by Bayer. The Dutch Medicines Evaluation Board (MEB) will be the regulatory lead and will communicate with the PRAC as needed regarding this study. The MEB and Bayer have agreed that Bayer will be responsible for liaising with the generic companies, and the study will share this common core protocol. To meet the study objective, a physician questionnaire will be developed and administered to physicians prescribing brand Diane-35 or its generics to assess their knowledge and understanding of the key safety information in this material. The educational material, Diane-35 Patient Card and Prescriber Checklist is included in Annex 3.

8 Research Question and Objectives

The primary objective of this study is to measure physician knowledge and understanding of the key information outlined by the PRAC and included in the educational material for Diane-35 developed by Bayer. Specifically, the following objectives will be addressed:

- Investigate whether physicians have received any educational material related to Diane-35 or its generics
- Assess physicians' knowledge and understanding of key safety information pertaining to the patient information card
- Assess physicians' knowledge and understanding of key safety information pertaining to the following areas:
 - Contraindications relevant to thromboembolism
 - Risk factors for thromboembolism
 - Signs and symptoms of thromboembolism

9 Research Methods

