9.3 Variables

A questionnaire will be developed to elicit responses measuring physician knowledge and understanding of the key information included in the Diane-35 educational material. This questionnaire will contain closed-ended multiple choice questions, with no free-text response fields, eliciting responses measuring physician knowledge and understanding of the key information in the Diane-35 educational material. The physician questionnaire will include items in the following content areas:

- The approved indication of Diane-35 and its generics
- Contraindications relevant to thromboembolism (i.e., current VTE, ATE, or cerebrovascular accident; history of VTE, ATE, or cerebrovascular accident; and selected comorbid conditions)
- Risk factors associated with thromboembolism (e.g., obesity, prolonged immobilisation, surgery, positive family history, age, smoking, selected comorbid conditions)
- Signs and symptoms of a thrombus (e.g., unusual unilateral leg pain; sudden severe pain in the chest; sudden breathlessness, visual disturbances; weakness or numbness in face, arm, or leg)

The questionnaire will include additional items to characterise the physicians and their practices (e.g., physician specialty, years in practice, patient volume) and investigate physician receipt and use of any educational materials related to Diane-35 or its generics.

Data from the questionnaire responses will be analysed to ascertain the level of physician knowledge and understanding stratified by country and other relevant characteristics (e.g., physician specialty).

The final version of the questionnaire is included in Annex 3.

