9.7 Data Analysis

Data analyses will be descriptive and focus on summarising questionnaire responses to individual questions among logical groupings of response items (e.g., Physician and Practice Characteristics, Physician Prescribing Practices). Results across all countries will be presented as well as stratified by country and possibly other variables, such as physician specialty and experience with Diane-35 or its generics. A detailed analysis plan describing the planned analysis of the physician questionnaire and data presentation, including table shells, will be developed prior to starting data collection. In addition to a description of the questionnaire data analysis, the analysis plan will describe comparisons of participants and non-participants, based on the data available on non-participants. Demographic (e.g., sex and age) and practice characteristics will be collected and compared amongst the eligible physicians (both for those who provided consent and for those who did not) as well as physicians who were not eligible to participate in the survey based on the screening question. In addition, the demographic and practice characteristics will be compared to characteristics available for prescribing physicians from other sources outside the survey data collection efforts.

Descriptive tables summarising demographics, questionnaire response results, and other available characteristics will be generated for the physicians, stratified by country and other variables of interest (e.g., physician specialty). For continuous-type data, the mean, standard deviation, median, and range will be presented. For categorical data, frequencies and percentages will be reported. The specific tables to be produced will be included in the analysis plan. An exploratory analysis will be conducted to evaluate predictors of physician knowledge level.

Typically, questionnaire data are mostly complete, and each question will be analysed individually among those participants who respond. However, as part of the analysis plan, we may establish a threshold of data required for a participant's questionnaire to be included in the analysis (e.g., completion of at least 11 of 14 knowledge questions).

The analysis plan will also describe the following:

- Analysis of subgroups
- Methods for handling missing data
- Level of statistical precision

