Annex 3.

Additional Information

Patient information card:35
Prescribers' Checklist:37
Physician Questionnaire **Error! Bookmark not defined.**

Patient information card:

Indication for which Diane-35 is prescribed:

Treatment of moderate to severe acne related to androgen sensitivity (with or without seborrhoea) and/or hirsutism, in women of reproductive age.

For the treatment of acne, Diane-35 should only be used after topical therapy or systemic antibiotic treatments have failed.

Since Diane-35 is also a hormonal contraceptive, it should not be used in combination with other hormonal contraceptives.

IMPORTANT INFORMATION ABOUT [PRODUCT NAME] AND RISK OF BLOOD CLOTS

All estrogen-progestagen combination products like [product name] increase the rare but important risk of having a blood clot. The overall risk of a blood clot is small but clots can be serious and may in very rare cases even be fatal.

It is very important that you recognise when you might be at greater risk of a blood clot, what signs and symptoms you need to look out for and what action you need to take.

In which situations is the risk of a blood clot highest?

- in the first year of using [product name] (including if you are re-starting use after a break of 1 month or more)
- if you are very overweight (body mass index over 30 kg/m²)
- if you are older than 35 years
- if you have a close family member who has had a blood clot at a relatively young age (e.g. below 50)
- if you have given birth in the previous few weeks

If you smoke and are over 35 years old you are strongly advised to stop smoking or use a non-hormonal treatment for your acne and/or hirsutism.

Seek medical attention immediately if you experience any of the following symptoms:

- Severe pain or swelling in either of your legs that may be accompanied by tenderness, warmth or changes in the skin colour such as turning pale, red or blue. You may be experiencing a **deep vein thrombosis**.
- Sudden unexplained breathlessness or rapid breathing; severe pain in the chest which may increase with deep breathing; sudden cough without an obvious cause (which may bring up blood); You may be experiencing a serious complication of deep vein thrombosis called a **pulmonary embolism**. This occurs if the blood clot travels from the leg to the lung.

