Sweating	 *		
Insomnia that started in the previous month			
Nausea or vomiting	 *		
Dizziness	 *		

Q21. A patient should be advised to seek immediate medical attention for which of the following symptoms of a possible cerebrovascular accident? Tick Yes, No, or I don't know for each symptom listed.

Symptoms	Yes	No	I don't know
Weakness or numbness of the face, arm, or leg, especially on one side of the body	 *		
Trouble speaking or understanding	 *		
A gradually increasing memory loss over the past year			
Sudden confusion	 *		

Sudden loss of vision or blurred vision	 *		
Hearing loss that has been increasing over the past year			
Severe headache/migraine that is worse than normal	 *		

The following questions ask about information you have received about Diane-35 or its generics.

Q22. Which of the following material(s) have you received?

Tick **all** that apply.

- Dear Healthcare Provider Letter for Diane-35 and/or its generics
- Diane-35 Patient Card
- Diane-35 Prescriber Checklist
- Other [PROGRAMMING NOTE: SKIP TO Q24]
- None of the above [PROGRAMMING NOTE: SKIP TO Q24]

[PROGRAMMING NOTE: ONLY DISPLAY RESPONSES THAT WERE TICKED IN Q22]

Q23. How helpful were these materials to you in treating and educating your patients?

Materials	Not at all helpful 1	2	3	Extremely helpful 4
Dear Healthcare Provider Letter for Diane-35 and/or its generics				
Diane-35 Patient Card				

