Diane-35 Prescriber Checklist				

Q24. In the past 3 months, for how many total patients have you prescribed Diane-35 for the treatment of acne or hirsutism?

- None
- 1 to 3 patients
- 4 to 6 patients
- 7 to 10 patients
- 11 to 15 patients
- More than 15 patients
- I'm not sure

Thank you for completing the questionnaire!

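### In Q22–Q24 the card, checklist and prescribing items name only Diane-35, and ticking Other skips the helpfulness ratings even for named materials the physician has ticked

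*Protocol*

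**What the plan says.** The first specific objective in section 8 is: "Investigate whether physicians have received any educational material related to Diane-35 or its generics". Section 9.2.1 admits a physician who prescribed the brand or a generic version to at least one patient in the past 6 months. Section 9.7 foresees results "stratified by country and possibly other variables, such as physician specialty and experience with Diane-35 or its generics".

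The Annex 3 questionnaire collects receipt, helpfulness and recent prescribing in Q22–Q24. The sentence that introduces Q22 refers to the brand and its generics. The options then differ:

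- The letter option covers both: "Dear Healthcare Provider Letter for Diane-35 and/or its generics".
- The card option does not: "Diane-35 Patient Card". The checklist option is worded in the same brand-only way.
- Q22 accepts more than one answer, and its fourth option is "Other [PROGRAMMING NOTE: SKIP TO Q24". The none option carries the same skip.
- A note before Q23 says to display there only the responses ticked in Q22. Q23 has rows for the letter, the card and the checklist, with the same wording as in Q22, and no row for Other.
- Q24 asks: "In the past 3 months, for how many total patients have you prescribed Diane-35 for the treatment of acne or hirsutism".

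**The concern.** This is a joint study on behalf of a group of marketing authorisation holders. Section 7 says that the generics are sold under several trade names. The patient card in Annex 3 is headed "IMPORTANT INFORMATION ABOUT [PRODUCT NAME] AND RISK OF BLOOD CLOTS", and the prescriber checklist carries the same kind of placeholder. A card or checklist bearing a name other than Diane-35 is therefore foreseeable, and Q22 has no option that fits it.

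Three things are at stake:

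- **Receipt by type of material.** A physician who holds only a generic-named card or checklist may not be counted for that item.
- **Helpfulness.** The skip attached to Other can remove ratings of materials that the physician did receive and tick.
- **Recent prescribing.** An eligible physician who prescribes only generics would truthfully report no patients in Q24.

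None of this can be repaired after collection. Section 9.3 describes a questionnaire "with no free-text response fields", so Other cannot be resolved later. Section 9.6.1 does not let participants return to earlier answers, and section 9.6.2 warns that correcting self-reported data may be impossible.

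**Working it through.** No stated figure is in question and no arithmetic applies. The check sets the scope of each item beside the scope of the study, then follows the routing for each kind of respondent.

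**Scope**

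| Element | Brand | Generics |
|---|---|---|
| Receipt objective (section 8) | yes | yes |
| Eligibility (section 9.2.1) | yes | yes |
| Possible experience stratifier (section 9.7) | yes | yes |
| Introduction to Q22 | yes | yes |
| Q22 and Q23, letter | yes | yes |
| Q22 and Q23, card | yes | not named |
| Q22 and Q23, checklist | yes | not named |
| Q24 | yes | not named |

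Because the letter option names the generics and the two options after it do not, a careful respondent may take the difference as intended.

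**Routing, read literally**

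1. *Letter received, Other not ticked.* Receipt and rating are recorded correctly for brand and generic users.
2. *Diane-35 card or checklist received by a prescriber of generics, Other not ticked.* Recorded and rated correctly.
3. *Only a generic-named card or checklist received.* The physician can tick Other (receipt of something is recorded, but the type is lost and no rating follows), tick none (receipt is lost), or choose the Diane-35 item as the nearest match (counted, but under a label that is not literally true).
4. *A named item and Other both ticked.* The skip sends the physician to Q24, while the display note calls for Q23 with the named item. The two notes conflict. If the skip prevails, the rating of the named item is lost, for brand and generic users alike.
5. *Only generics prescribed in the past 3 months.* The literal answer to Q24 is none, although the physician is eligible.

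Case 5 cannot be detected from Q24 alone. Eligibility looks back 6 months and Q24 looks back 3, so an answer of none is also legitimate for a physician who last prescribed 4 to 6 months ago. Active prescribers of generics and inactive prescribers would share one category.

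**The case against.** The strongest reply is that the exposure is limited, and much of it stands.

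- Section 7 says that the material goes to professionals expected to prescribe the brand or its generics, so a prescriber of generics may well hold the Diane-35 card (case 2). The primary objective also concerns the material that Bayer developed for Diane-35, so naming those items is partly on target.
- A physician who ticks Other has still reported receiving something.
- The skip was plausibly meant for those who tick Other alone, since Q23 has no row for it. Section 9.6.2 provides for logic checks and user acceptance testing, which might catch the conflict. Helpfulness is not a listed objective.
- Restricting Q24 to acne or hirsutism matches the approved indication and is no fault.

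A reader might go further and infer that recorded receipt falls in proportion to the share of recipients who hold only generic-labelled material. If that share is assumed to be 10% to 50%, a true 80% would be recorded as 0.80 × 0.90 = 72% down to 0.80 × 0.50 = 40%, and a true 60% as 0.60 × 0.90 = 54% down to 0.60 × 0.50 = 30%. The document does not support this as the effect. It gives no such share, and the formula counts every such holder as having received nothing, as if none had ticked Other, the letter or the nearest Diane-35 item. The figures are a worst case on an unsupported assumption.

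A reader might also infer that the experience strata will place active prescribers of generics in the zero group. That is not established either. Nothing says that Q24 defines the stratum, section 9.7 offers it only as a possibility, section 9.2.1 describes a screening question that covers generics, and the questionnaire as shown begins at Q8.

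What the reply does not remove is that the wording of two Q22 options and of Q24 is narrower than the objective and the eligible population, and that two programming notes contradict each other.

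**Conclusion.** The point holds as a fault of wording and routing, of moderate severity. Card- and checklist-specific receipt and recent prescribing may be under-recorded for users of generics. Helpfulness ratings may be lost for any physician who ticks Other together with a named material.

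The size cannot be derived from the document. It depends on how many physicians hold only generic-named items, how they answer when no option fits, how many tick Other in addition to a named item, and which programming note prevails. For Q24 the conclusion is also conditional: an item among Q1–Q7 on generic prescribing would reduce the loss, and the absence of those items from the text is not held against the plan.

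The documents do not support saying that receipt as a whole is misrecorded, because the introduction to Q22 and the letter option include the generics and Other still registers receipt. The knowledge questions Q8–Q21, which carry the primary objective, are untouched.

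**What to change.** - In Q22, extend the card and checklist options to Diane-35 or its generics, as the letter option already does, and change the matching rows of Q23.
- In Q24, ask about Diane-35 or its generics.
- Replace the skip on Other with one condition: omit Q23 only when none of the three named materials is ticked. This agrees with the display note.
- Make the none option exclusive.

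Once the options are widened, Other holds only further kinds of material. A Q23 row for it is needed only if its helpfulness is also wanted.

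The cost is a few words in three questions in each language version, one routing condition in the data capture system with its test, and whatever notice the review board requires, since section 10 has it review the questionnaires. No extra respondents are needed. The change has to be made before the first country opens, because no later analysis can recover an answer that was not collected.
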